Non-auditory side effects are a relatively common occurrence from ABI stimulation and are usually related to activation of the neural tissue in the region of the implant. Toh and Luxford reported non-auditory side effects in 42% of multichannel ABI users (44). Colletti et al (48) reported that ipsilateral body tingle was observed in 2 children (6.9%), facial nerve stimulation in 2 (6.9%), dizziness in 1 (3.4%), headache in 1 (3.4%), and throat tingle/tickle in 1 (3.4%) child. In adults, ipsilateral body tingle was observed in 10 subjects (8.7%: 7 NFII and 3 non-tumor), facial nerve stimulation in 6 (5.2%: 4 NFII and 2 non-tumor), dizziness in 15 (19%: 9 NFII and 6

non-tumor), headache in 5 (6 %: 3 NFII and 2 non-tumor), and throat tingle/tickle in 8 (9.6%: 5 NFII and 3 non-tumor). These side effects are all alleviated with selective electrode deactivation. Re-activation of the offending electrode over time usually resolved the issue.

TABLE 2. Complications in ABI patients.

	NFII Ad	Non-tumor	
		Ad	Ch
Major complications			
Mortality (unrelated to ABI)	3	0	0
Cerebellar contusion	1	0	1
Permanent facial palsy	1	0	0
Meningitis	1	2a	1a
Lower cranial neuropathy	2	0	0
Hydrocephalus	1	1	0
Pseudomeningocele	2	0	0
Cerebrospinal fluid leakage	6	1	0
Minor complications			
Transient hydrocephalus	7	1	0
Wound seroma	4	2	4
Minor infections	2	2	1
Balance problems	11	2	1
Infection around implant	2	2	0
Infection surgical flap	2	1	0
Transient facial palsy	8	0	0
Temporary dysphonia and difficulty in swallowing	0	0	1
Headache	8	3	0
Flap problems	2	0	0
Non-auditory side effects	28	16	7

(a) Approximately 2 years after ABI activation.
Ad, adults; Ch, children.

Benefits and Risks

The benefits and risks of ABI in children are listed in TABLE 3 based on a compilation of previous literature using the ABI in the proposed population, personal experience with posterior fossa surgery at UNC and in the literature, and the experience of children that have received cochlear implants for severe to profound hearing loss. The sections above detail the outcomes from the medical literature and the individual benefits and risks as well as others not previously mentioned are in the table below.

TABLE 3. Potential Benefits and Risks of ABI

Potential Benefits	Potential Risks

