Risks and complications from ABI surgery are expected to be uncommon but can potentially be serious. Major complications such as bleeding in or around the brain including major cerebellar contusion should be very unlikely since extensive dissection, such as is undertaken in tumor surgery, will be unnecessary. In tumor surgery, the risk of major bleeding is well below 2%. At UNC, we have had one major posterior fossa hemorrhage in our last 164 acoustic tumor cases (0.6%). In a large series (n=4400) from the literature of non-tumor posterior fossa craniotomies performed for microvascular decompression, the risk of cerebellar injury (parenchymal bleeding/contusion) was less than 1% and major other hemorrhage was much less common. Thus, the risk for intracranial hemorrhage and/or cerebellar injury with subsequent stroke is small. CSF leakage from the wound or from the nose (rhinorrhea) can also occur. This will likely be the most common surgical complication. Given the lack of need for internal auditory canal drilling (as in acoustic neuroma surgery); the leak risk will be well below 10% (that seen for acoustic neuroma surgery in the literature). At UNC, our leak rate was <8% (n=13) for our last 164 acoustic tumor cases. In the microvascular decompression literature, the CSF leak rate is <2%. The etiology of rhinorrhea, should it occur, will also be very clear since internal auditory canal drilling is not required in this surgery. Rhinorrhea will arise from exposed mastoid air cells in the cranial opening. Similarly, the risk of cranial nerve injury will be unlikely since the anatomy will not be obscured by pathology such as tumors or infection. While cranial nerve 8 and 9 border the lateral recess of the 4th ventricle (Foramen of Luschka), neural dissection will likely be mostly unnecessary and not obscured by tumor. Infection risk can include meningitis. This risk is less than 2% as a complication from craniotomy in the literature. The risk of device loss from infection is also very small.

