It is anticipated that this pilot study will be used to demonstrate safety and give some idea regarding efficacy. However, a larger scale clinical trial will be needed beyond the pilot study to demonstrate surgical safety on a broader scale (across surgeons and institutions) and the utility of the device for the intended auditory benefits. Ten subjects should be a sufficient sample size to demonstrate safety. If the European data is correct regarding complication rates in children, a single CSF leak might occur in one subject and non-auditory side effects can be expected to occur in roughly 20% of children or 2 subjects in this study. This number seems to be a conservative and reasonably small number to demonstrate these effects. Non-auditory stimulation is not serious and can be programmed around with simple changes in device programming during activation. For speech perception and production, the within subject design should allow us to see some benefit from the device if effective. Since the children are deaf, any development of significant open or closed set perception (beyond patten perception) would be attributable to the device. Similarly for language outcomes although these will take longer time to develop. Thus, the safety numbers are the drivers in powering this study.

The data will be recorded in patient-specific binders on a case-by-case basis after each subject encounter. All data will be entered in to the secure, File Maker Pro, customized database for CI research housed in the Department of Otolaryngology-Head and Neck Surgery that is currently in use. The lead investigator will cross check the data prior to approval for review. The data will be exported by desired fields to an Excel spreadsheet (Microsoft) for further analysis. Statistics will be carried out using SPSS software. If needed, statistical consultation will be sought at the University TRACS or Odum Institute.

Study Endpoints

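### The one-in-ten CSF leak figure offered in support of n = 10 does not follow from the plan's own paediatric data, and ten leak-free children would not show a low leak rate

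*Combined protocol and SAP*

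**What the plan says.** The sample-size paragraph in Data and Analysis states: "Ten subjects should be a sufficient sample size to demonstrate safety". It supports this with two expected counts. The first is "If the European data is correct regarding complication rates in children, a single CSF leak might occur in one subject". The second is "non-auditory side effects can be expected to occur in roughly 20% of children or 2 subjects in this study". It adds "This number seems to be a conservative and reasonably small number to demonstrate these effects" and concludes "Thus, the safety numbers are the drivers in powering this study". It gives no alpha, power, precision target or acceptable complication rate.

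The European data are not identified there. Table 2 tabulates complications from a European series of 114 retrosigmoid ABI operations. Its row "Cerebrospinal fluid leakage" shows 6 for NFII adults, 1 for non-tumor adults and 0 for non-tumor children. The section on complications gives the denominators: 34, 49 and 29. That section, and the later human subject protection text, also cite one leak in a child from a separate report, without a denominator.

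The Potential Risks text says "the leak risk will be well below 10% (that seen for acoustic neuroma surgery in the literature". It also gives 13 leaks in the site's last 164 acoustic tumor cases, and under 2% in the microvascular decompression literature.

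**The concern.** The plan says that safety counts drive the sample size, so those counts should follow from the source they invoke. One does and the other does not. The leak figure implies about 10%, while the children's column shows none in 29 and the plan's own risk section expects a rate well below that.

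The effect is on interpretation. Study Endpoints judges safety case by case, with no numerical threshold, so the two expected counts are the only numerical benchmark for this cohort's safety results. Against a benchmark of one leak, a leak-free series would look better than expected and could be read as showing safety. At most of the rates the plan cites, it would simply be the more likely result, and it would say little about the true rate.

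**Working it through.** **Inputs.** n = 10 (Data and Analysis). Leaks: 0/29 non-tumor children, 1/49 non-tumor adults and 6/34 NFII adults (Table 2 and the complications section); 2/31 and 2/61 in two other ABI series (complications section); 13/164 and under 2% (Potential Risks). Non-auditory effects: 7 in the children's column of Table 2. The 5% rate is an assumption, used as one reading of a risk well below 10%.

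**Step 1: reproduce the plan's two counts (expected count = n × p).**
- Non-auditory effects: 10 × 0.20 = 2.0, and from Table 2, 10 × 7/29 = 2.4. This agrees. The chance of at least one is 1 − 0.8^10 = 89% at 20%, and 94% at 7/29. (The 7 is treated as 7 children; it equals the sum of the listed symptoms, 2 + 2 + 1 + 1 + 1, so some may share a child.)
- CSF leak: 10 × 0/29 = 0, not 1. Of the Table 2 columns, only NFII adults reach one or more (10 × 6/34 = 1.76).

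**Step 2: how far 0/29 is from 10%.** The exact two-sided 95% upper limit is 1 − 0.025^(1/29) = 11.9%. If the true rate were 10%, the chance of no leak in 29 would be 0.9^29 = 4.7%. So 10% is inside the two-sided interval, near its upper end, but is not what the series suggests.

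**Step 3: chance of at least one leak in ten, 1 − (1 − p)^10.**

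| Rate | Source | Expected leaks | Chance of at least one |
|---|---|---|---|
| 1.3% | 1/78, all non-tumor patients | 0.13 | 12% |
| 2% | microvascular decompression ceiling | 0.20 | 18% |
| 3.3% | 2/61 | 0.33 | 28% |
| 5% | assumed | 0.50 | 40% |
| 6.5% | 2/31 | 0.65 | 49% |
| 7.9% | 13/164, site's tumor surgery | 0.79 | 56% |
| 10% | implied by the plan's figure | 1.00 | 65% |

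The chance falls below one half when p < 1 − 0.5^(1/10) = 6.7%.

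**Step 4: include the extra paediatric leak.** Its denominator is not given. Assuming 5 to 30 children, the pooled rate is 1/34 to 1/59, or 2.9% to 1.7%, and the chance of a leak in ten is 26% to 16%. The rate stays far below 10%.

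**Step 5: what zero in ten shows.** The exact two-sided 95% upper limit is 1 − 0.025^(1/10) = 30.8% (one-sided 95%: 1 − 0.05^(1/10) = 25.9%).

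**The case against.** The best defence is that the sentence is soft and little hangs on it. It says that a leak might occur, and keeps the firmer wording for non-auditory effects. It does not name its source. No test, threshold or stopping rule uses the count, complications are summarised descriptively, and the same paragraph defers broader safety to a larger trial. An over-high risk forecast is also cautious. All of this is fair and limits the consequences. It does not make the figure follow from paediatric data, nor reconcile it with the risk section.

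A reader might go further in three ways that the documents do not support.

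- *That a leak would probably go unseen in ten children.* This depends on the rate. It holds below 6.7%, but the site's tumor-surgery rate gives 56%, and 0/29 does not exclude 10%. The Benefits and Risks text says that no surgical cohort is truly comparable, and Surgical Closure notes that the array cable prevents a fully watertight dural closure. Both are reasons not to lean only on the lowest rates. If enrolment is 15 (10 plus 5 in the opening purpose statement), the chance is 26% at 2% and 54% at 5%.
- *That the whole rationale for n = 10 fails.* The leak is one of two named events, and the other reproduces and would very probably be seen.
- *That the risk section errs in saying of a leak "This will likely be the most common surgical complication".* Wound seroma was commoner in the children's column (4/29, about 1.4 per ten), but that sentence is a forecast, and four seromas in one series do not refute it. Nor is the word conservative at fault: it most naturally describes the number of subjects.

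**Conclusion.** Wrong as written, with limited scope. An expectation of about one leak in ten is not supported by the tabulated European paediatric data (0/29, 95% CI 0 to 11.9%) and conflicts with the plan's own statement of leak risk. The non-auditory figure stands. Because the plan says that safety counts drive the sample size, the larger consequence is for the conclusion: a leak-free series of ten would not by itself demonstrate a low leak rate.

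This rests on taking the unnamed European data to be the Table 2 series. That is an inference, but a reasonable one, since the table also yields the plan's other figure. It also rests on independent children with a common leak rate. With 15 children and no leak, the upper limit would be 1 − 0.025^(1/15) = 21.8%, which leaves the conclusion in place.

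**What to change.** Replace the leak sentence in Data and Analysis with wording such as:

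> In the tabulated European series no CSF leak occurred in 29 non-tumor children (exact 95% CI 0 to 11.9%); one further paediatric leak is reported elsewhere without a denominator. In ten children the chance of observing at least one leak is 12 to 18% at a rate of 1.3 to 2%, 40% at an assumed 5%, 49% at 2/31 and 65% at 10%. No leak in ten would remain compatible with a rate up to 30.8% (two-sided 95%), so a leak-free series would not by itself demonstrate a low leak rate.

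Qualify the claim that ten subjects suffice to demonstrate safety in the same terms, and keep the non-auditory figure. Optionally, note wound seroma as the commonest surgical event in the children's column. If enrolment is 15 rather than 10, recompute for that number.

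The cost is a few sentences of protocol text and a more modest safety claim. Enrolment, visits and data collection are unchanged.

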The purpose of this feasibility study is to demonstrate the safety and efficacy of the Nucleus 24 Multichannel Auditory Brainstem Implant (ABI, Cochlear Corp, Sydney, AUS) in children who do not have the diagnosis of neurofibromatosis type II (NFII), and who have either experienced failed cochlear implantation (CI) or have been unable to receive a CI secondary to cochlear or cochlear nerve disorders. These conditions can include: developmental or acquired cochlear nerve deficiency (CND), cochlear aplasia (Michel), post-meningitis cochlear ossification, or cochlear malformation. This study proposes to implant up to 10 pre-linguistic young children (18 mos to 5 yrs. of age) and 5 post-linguistic children (<18 yrs of age) with the Nucleus 24 Multichannel ABI in an attempt to demonstrate safety of the surgical procedure, tolerance of device stimulation, and the potential for auditory benefit beyond that experienced with their CI. This study will provide the preliminary experience for a larger scale clinical trial.

Regulatory Status of the Investigational Device

Data supporting the safety and effectiveness of the Nucleus 24 ABI were provided to the United States Food and Drug Administration (FDA) in March 2000, as part of a Premarket Approval Application. On July 21, 2000, the Agency's Ear, Nose and Throat (ENT) Advisory Panel unanimously recommended that FDA release the Nucleus 24 ABI for use by individuals with NFII above the age of 11 years. Cochlear Americas received a letter of approval from the Agency in October 2000 (PMA No P000015). The letter is enclosed.

The Nucleus 24 ABI features a multichannel electrode lead that terminates in twenty-one, 0.7 mm platinum disk-electrodes. The 21 platinum contacts are arranged on the surface of a silicone rubber pad in three rows of seven contacts and are surgically placed on the surface of the brainstem; specifically, on the surface of the cochlear nucleus.

Background and Rationale

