The only absolute contraindication to CI is an absent cochlea or an absent cochlear nerve. In addition, patients at risk for lower levels of performance include those with anatomic conditions that adversely affect the electrode-neural interface such as developmental labyrinthine malformations and cochlear ossification and fibrosis secondary to meningitis. While the diagnosis of cochlear (i.e. Michel) aplasia is clear clinically, the diagnosis of cochlear nerve aplasia is made somewhat more challenging by the spatial resolution of current imaging modalities (26-29). Because of this uncertainty, the term cochlear nerve deficiency (CND) was coined to refer to the situation where the cochlear nerve is small or absent on high resolution magnetic resonance imaging (MRI), or where the bony cochlear nerve aperture and canal are small or absent on temporal bone computed tomography (CT). The clinical diagnosis of CND includes these imaging findings in the setting of profound hearing loss (29, 30). Auditory brainstem response testing that shows a present cochlear microphonic but absent neural waves can support the diagnosis (29).

In an effort to provide hearing to deaf children who have inner ear malformations, CND, or ossification from meningitis, CI has been undertaken over the years (30). This might be considered the standard of care today for those who desire spoken language communication. Results of these interventions suggest that most children with CND gain some sound awareness from these devices using higher levels of electrical stimulation. However, achievement of open set speech perception for the purposes of speech and language development has been largely unsuccessful, probably as a result of a poor electrode-neural interface and other associated conditions (30-33). In the study from our institution, only 19% of children with CND developed any open set speech perception using their CI, and none of these children were able to communicate using auditory-only information (i.e. all used some supplemental sign language).

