In theory, children would be better candidates than adults for an ABI since they have substantial developmental plasticity and have no auditory memory that requires precise matching

of signals. Colletti and colleagues in Verona, Italy, have placed *ABIs in children* without NFII and have summarized their experience in 2008 (41). In that study, 26 children (17 in Verona; 9 in other countries) aged 14 months to 16 years received an ABI for different tumor and non-tumor diseases between 1996 and 2006. Etiologies included cochlear nerve aplasia with or without associated inner ear malformations (n=19), NFII (n=2), incomplete cochlear partition (n=2), auditory neuropathy (n=1), post-meningitis ossification (n=1), and temporal bone fracture with nerve avulsion (n=1). Fourteen children had a variety of other disabilities including: mild motor delay (n=8), learning disability (n=7), behavioral impairment (n=7), cognitive delay (n=8), language delay (n=6), and 2 with visual impairment. Six children received previous CIs with no auditory results. All were operated through a retrosigmoid craniotomy, and there was one reported major complication (detailed below). Results showed that all children consistently use their devices (avg. 8 hrs./day) and demonstrated gradual improvement in communication skills, showing more attention and interest in school and at home. From an auditory perspective, 20 pre-linguistic and 4 post-linguistic children have environmental sound awareness, detection of instrumental sounds and lip-reading enhancement; 3 pre-linguistic and 2 post-linguistic children achieved bi-syllabic word recognition as well as understanding of simple commands, but only one post-linguistic child had open set recognition (average 50% correct responses) and can perform the speech tracking test. Cognitive testing in a subset of 9 children using the ABI demonstrated improved selective visual-spatial attention (form completion subtest) and fluid (multisensory) reasoning (repeated patterns subtest) when compared to a group of 4 congenitally deaf children without an auditory assistive device.

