This study is an early feasibility study of the Nucleus 24 ABI in children without NFII. It will be conducted as a repeated-measures, single subject experiment with up to 10 replications (i.e. 10 total subjects). A single-subject research design was chosen (in which each subject serves as their own control) in order to accommodate the heterogeneity that is well known to characterize auditory prosthesis research. Post-operative evaluations will be conducted at the initial activation and at 1, 3, 6, 12, 18, 24, 30, and 36-month intervals post-activation. A 36-month follow-up was chosen in an effort to demonstrate the emergence of open-set speech perception abilities prior to study cessation. Experience in the CI literature has shown that a minimum of 2 years of device usage is required for children with pre-lingual hearing impairment to develop some open-set speech perception abilities (50). Blinding or masking procedures are not included in the design, as the presence/absence of a brainstem implant cannot be easily concealed from the device recipients and/or clinical investigators.

Preoperative measures will include high-resolution brain MRI, temporal bone CT and standardized, developmentally appropriate audiological and speech and language development test batteries. Children between 18 mo and 5 yrs of age with one of the anatomic conditions mentioned below and a present and patent cochlea will have previously received a CI as a precondition prior to consideration and will have demonstrated very limited to no benefit from

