the device based on a lack of development of significant closed set (more than pattern perception) or open set speech perception, and failure to achieve developmentally appropriate language growth during the follow up period. Those without a present or patent cochlea will be implanted with the ABI without the need for previous CI. Post-linguistic children (<18 yrs) will have had a CI but lost or lacked benefit from an appropriate CI and have no potential for revision CI surgery to improve their condition. The side/ear contralateral to the previous placed CI will be chosen, unless not possible (eg. bilateral CIs), to avoid potentially same-side, unwanted surgical and processor interactions as well as to allow comparison of performance in the follow-up period. If ABI needs to be considered ipsilateral to the previous CI, removal of the CI will need to be considered. Surgical interaction would be the issue of needing to operate in and around the CI device putting it at risk of damage. Unwanted processor interactions would be problematic if the receiver stimulator of the previous CI and the ABI were located in the same region. The ABI processor headpiece might be attracted to the CI receiver stimulator.

Following implantation of the investigational device and at least 4-6 weeks of healing, the ABI will be activated in a controlled setting and auditory performance assessed at the previously proposed intervals (1, 3, 6, 12, 18, 24, 30, 36 months). Subjects will be evaluated using the Nucleus Speech Processor and programmed with an approved sound processing strategy. Post-operative auditory function will be evaluated using behavioral audiometry and commonly used, developmentally appropriate measures of speech perception, speech production and language. Auditory function will also be assessed using electrophysiological tests at appropriate intervals.

SPECIFIC AIMS

Aim 1: Demonstrate the safety of ABI surgery in children.

Aim 2: Demonstrate the development of sound awareness and improved speech understanding among children implanted with the ABI when compared to their baseline skills.

Aim 3: Demonstrate the development of oral language skills following the use of the ABI that were not evident prior to its use.

Methods and Subjects

Up to 10 subjects will be enrolled in the study at the sponsoring location. Qualified subjects must meet the following inclusion criteria and must not exhibit any of the exclusion criteria.

Inclusion Criteria

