Study endpoints are based on the 3 specific aims. For safety, this will be determined on a case-by-case basis and any adverse events will be reviewed with the IRB and the data monitoring board (2 individuals appointed). Should the adverse events be deemed unacceptable to the investigators, the IRB, or the monitoring board, this would be sufficient terms for study discontinuation. Three years of follow up was chosen to provide adequate time for the emergence of open-set speech perception abilities in the pre-lingual cohort of children. In studies of prelinguistic children undergoing CI, at least 2 years of follow-up is needed to demonstrate emergence of these skills (23). If no open set perception is demonstrated at 3 years, this seems to be good evidence for a lack of benefit on this measure. In general, speech and language measures should track speech perception abilities. While the full emergence of these skills can take

somewhat longer to develop, it is anticipated that early emergence will be evident if speech perception is developing. While not anticipated, a clear lack of benefit from the device (such as no sound awareness) among multiple subjects would also be consideration for stopping the study. Study recruitment is expected to be slow at 1-3/year. This will not stop the study.

Human subject protection measures

Risks and measures to minimize risk. There is limited psychological, social, legal and economical risk to patients for participating in this study. The potential for a confidentiality breach is rare. All children and their parents will be treated confidentially according to HIPAA and its requirements. All discussion of the results of the intervention for the purposes of results reporting will be made anonymously.

The physical risks include medication side effects, pain, discomfort, or injury from participation. The potential risks from participation are likely (10-25%) and dependent on the consequences in question. The potential complications have been detailed above.

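### No open-set perception at 3 years is to be read as good evidence of no benefit on that measure, yet 0 of 10 children would be compatible with a true rate of up to about 26% to 31%

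*Combined protocol and SAP*

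**What the plan says.** Study Endpoints explains that three years of follow-up was chosen to give pre-lingual children time to develop open-set perception, and that cochlear implant (CI) studies needed at least two years. It then states how a null result will be read: "If no open set perception is demonstrated at 3 years, this seems to be good evidence for a lack of benefit on this measure". No interval, threshold or minimum number of evaluable children is attached.

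On numbers, the Methods and Subjects section says "Up to 10 subjects will be enrolled in the study at the sponsoring location", and the Protocol section agrees. The opening statement of purpose differs: "This study proposes to implant up to 10 pre-linguistic young children (18 mos to 5 yrs. of age) and 5 post-linguistic children", which makes 15. The sample-size reasoning in Data and Analysis rests on complications and side effects: "Thus, the safety numbers are the drivers in powering this study".

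Two earlier open-set results are cited. Background and Rationale reports that, at the investigators' institution, "only 19% of children with CND developed any open set speech perception using their CI" (CND is cochlear nerve deficiency). The section on experience in patients without NFII describes 26 children with an auditory brainstem implant (ABI), among whom "only one post-linguistic child had open set recognition".

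**The concern.** Length of follow-up and number of children answer different questions. Three years may be long enough for a child who will develop open-set perception to show it. That does not tell us how many children must be observed before an absence of successes says something about the device. Success was infrequent in both series the plan cites, and with an infrequent outcome a small group can contain no successes although the device helps some children.

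What is at stake is the conclusion reported from the pilot. Under the sentence as written, a cohort with no successes could be described as good evidence against open-set benefit when the data leave room for a rate of a quarter or more.

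**Working it through.** **The plan's own figure.** The only arithmetic behind the sample size is an expected count: "non-auditory side effects can be expected to occur in roughly 20% of children or 2 subjects in this study". This reproduces, since 10 × 0.20 = 2. It concerns side effects. No power, precision or success threshold is given for open-set perception, so there is no efficacy figure to reproduce.

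**Inputs.**
- n = 10: the maximum number of pre-linguistic children under either enrolment statement.
- n = 15: all children in the statement of purpose (10 + 5), pooled.
- n = 8 and n = 5: assumed, to show the effect of fewer evaluable children. Enrolment is up to 10, is expected at 1 to 3 per year, and families may withdraw.
- Confidence level 95%: Data and Analysis uses it for comparisons with baseline but does not say whether it is one- or two-sided, so both are shown.
- Reference rates, for context only: 19% (CI, children with CND) and 1/26 = 3.8% (published ABI series in children).

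**Formulas for zero successes in n children.**
- One-sided exact upper limit: 1 − 0.05^(1/n)
- Two-sided exact (Clopper-Pearson) upper limit: 1 − 0.025^(1/n)
- Probability of no successes at true rate p: (1 − p)^n

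**For n = 10.**
- One-sided: 1 − 0.05^(0.1) = 0.259
- Two-sided: 1 − 0.025^(0.1) = 0.308
- At 19%: 0.81^10 = 0.122
- At 1/26: (25/26)^10 = 0.676

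| n | Upper limit, one-sided | Upper limit, two-sided | P(no successes) at 19% | P(no successes) at 1/26 |
|---|---|---|---|---|
| 5 | 45.1% | 52.2% | 34.9% | 82.2% |
| 8 | 31.2% | 36.9% | 18.5% | 73.1% |
| 10 | 25.9% | 30.8% | 12.2% | 67.6% |
| 15 | 18.1% | 21.8% | 4.2% | 55.5% |

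As a check by another method, the two-sided Wilson upper limit for 0/10 is 27.8%.

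**Who counts as a zero.** Data and Analysis assigns 0% on open-set tests to a child who cannot complete the test despite substantial implant experience. It labels open-set results as untestable when a child cannot do closed-set testing. A reported zero can therefore include children who never completed an open-set test, and n depends on how these children are handled.

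**The case against.** The strongest reply is that the sentence argues from duration within a single-subject design. Read child by child, it says that a child without open-set perception after three years has probably not gained it, and a binomial interval has no bearing on that. It is also hedged, limited to one measure, and set in a declared pilot. The hedging and the limited scope stand and keep the point modest. The child-by-child reading is possible, but the section defines study endpoints and the preceding text concerns the pre-lingual cohort and group studies of CI recipients. A cohort reading is the natural one, and nothing in the text rules it out.

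The reference rates are also open to challenge. The 19% comes from children with CND using a CI, whereas pre-linguistic children here who have a present or patent cochlea enter only after failing to benefit from one. The 26-child series included NFII, ages up to 16 years and 14 children with other disabilities, and its one success was post-linguistic. Neither is a matched control, and Aim 2 compares children with their own baseline. This stands, and the upper limits use neither rate.

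A reader might infer several stronger things that the documents do not support:
- **That the sentence is a futility rule which could block the larger trial.** No decision is attached to it. Data and Analysis says a larger trial will be needed, without making that depend on open-set results. The benefit-related ground for considering stopping is lack of benefit among multiple subjects, with absence of sound awareness as the example.
- **That zero successes is likely even if the ABI equals the CI.** At 19% the probability is 12% with 10 children.
- **That the section contradicts itself by saying these skills take longer to emerge.** That remark follows a sentence on speech and language measures and most naturally refers to them.
- **That a null result should count as lack of benefit only if the upper limit falls below 19%.** Zero of 10 can never meet that test, and it would import an unmatched comparator into an own-control design.

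**Conclusion.** The point holds for a cohort-level conclusion. With at most 10 pre-linguistic children, no successes would leave a true open-set rate of up to about 26% (one-sided) or 31% (two-sided) compatible with the data, and 45% to 52% if only 5 were evaluable. Pooling all 15 children lowers this only to 18% or 22%, and it mixes in post-linguistic children, who must already have had open-set perception. The two cited series show how far a null result depends on the true rate: 0/10 would occur 12% of the time at 19% and 68% of the time at 1/26.

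The limits assume independent children with a common success rate, a 95% level and complete assessment at 36 months. This is over-interpretation of a small sample. It is not an error in a calculation, and it does not affect the safety rationale for the sample size. A null result would still be informative, since it would make rates well above 31% implausible.

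**What to change.** Replace the sentence in Study Endpoints with wording such as:

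> The number of children with open-set perception at 36 months will be reported as x/n with an exact 95% confidence interval, separately for pre- and post-linguistic children, with children unable to be tested shown. Zero of 10 would be compatible with a true rate of up to about 31% and will not by itself be read as lack of benefit. Absence of open-set perception in an individual child after 3 years will be described for that child only.

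Reconcile the enrolment of 10 in total with the 10 plus 5 in the statement of purpose, so that n is clear for each group. State also which open-set result counts as a success, because the plan sets no threshold and x cannot be counted without one.

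No added visits, tests or children are needed. The cost is that the stated strength of a null result becomes less favourable.
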